## Rationale & background information

Stroke is one of the largest causes of adult disability in the world. Every year it is estimated that approximately 15 million people worldwide suffer a stroke; of these, 5 million die and another 5 million are left permanently disabled, placing a burden on families and communities. Around 20% of stroke survivors are under the age of 65 and hence are still a productive working age [1].

Rehabilitation is one of the most important aspects of care for patients following a stroke and is proven to affect the eventual level of recovery and independence achieved. Community stroke services that provide rehabilitation exist in the study region, and are able to provide support, lifestyle advice and risk factor assessment. Charitable organisation often provides a range of valued support services for stroke patients and their caregivers in the community. When patients leave the hospital quickly after stroke to receive intensive rehabilitation in their home environment it is called ‘Early Supported Discharge’ (ESD). This is usually for people who have milder disabilities after stroke and are able to move about unaided or with minimal help.

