## Study goals and objectives

The goal of this study is to assess the acceptance and validity of a new technology such as WeReha for home rehabilitation of patients following a stroke episode either in sub-acute or chronic phase. The investigation will be conducted in two different countries: two sites in Northern Ireland and one in Italy.

This study is part of the EU funded Magic PCP project [5], where three different companies will perform similar types of study. Every company will be assigned from September 2018 a trust in Northern Ireland and a site in Italy from among the following: Hospital Le Torrette, Ancona, University D'Annunzio, Chieti, ASL3 Pinerolo, Torino. Once a company has received approval for funds to perform the study (before September 2018), it will also be assigned the site in Italy and then it will apply for the Ethical Committee of that site. Every company is also required by the Magic PCP project [5] to provide 75 devices per country (150 in total). From now on, we will refer to the number of patients relevant to the Northern Irish site..

Let us define the terms and list assumptions we will use throughout the protocol:

- “enrolled patient”: a patient is considered enrolled in the study if they are within the inclusion criteria and voluntarily accept to participate and sign the consent form
- “active week”: a week in which the patient has performed at least three sessions with WeReha for a minimum of 15 minutes each (as measured by the software)
- “active patient”: a patient that has used the device for at least 4 “active weeks”
- “maximum time frame of usage”: 20 weeks, according to patients and clinicians feedback collected during our feasibility study (see [Safety Consideration](#) section)
- “end of usage”: if the participant does not have four active weeks in the first eight weeks of usage or the patient has reached the “maximum time frame of usage” or the patient has voluntarily decided to interrupt the study (drop-off)

The study aims to evaluate as a primary outcome quantifiable measure, the acceptance of technology, through analysis of the following:

- number of enrolled patients at the end of the trial period will be evaluated in order to understand the degree of acceptance of a technology such as WeReha, with the minimum target of 50 patients.
- number of “active weeks” with the device among the patients enrolled

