- average minutes of exercise per day conducted with the technology as an objective measure for activity participation
- acceptance of technology, based on the Technology Acceptance Model / TAM as in [11] and [33] provided to patients at the end of the study (see [Annex B](#)).

All previous measures will be evaluated in general and for 6 different age-gender groups (male and female below 55, between 55 and 70, above 70).

As secondary outcome measures we will assess objective scales and scores typical for stroke rehabilitation:

- the Barthel index (see [10], [19], [6], [8])
- the Modified Rankin Score (see [19], [30], [7], [8])
- 

These scores will be compared with standard values and the goal is to show equivalency or improvement from those standard values after the treatment with WeReha.

In addition, we want to demonstrate the logistical and economic benefits of the deployed solution. Dedicated figures (a nurse or physiotherapist hired to run the Clinical Trial research study as explained in the Methodology section) will objectively measure the time taken to training patients and caregivers before leaving the trial site with the device and the number of times patients contact the sponsor for technical assistance.

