#### **Primary Outcome Measures:**

- Total number of patients enrolled -> KPI: minimum 50 patients enrolled;
- Total number of active patients -> KPI: minimum 40 active patients;
- Total number of patients who drop off, meaning that started the study and had less than 4 active weeks
- Average number of active weeks for each patient: the average number of active weeks is evaluated as the total number of active weeks divided by the number of patients enrolled -> KPI: 8 weeks (excluding drop off before 4 weeks)
- Activity participation, measured in average minutes per day dedicated to exercises with WeReha (measured during active weeks only) -> KPI: min. 45'/week
- Acceptance of the rehabilitation platform WeReha by the patient, evaluated through a questionnaire completed at the end of the study by every participant who consents to the study (see attachment ... )
- Previous results will be analysed on different age/gender groups. Age groups are: <55, 55-70, 70-85 both for male and female, for a total of six groups. Target would be to enroll patients within these groups as homogeneously as possible, but since we cannot foresee patients distribution there are no KPIs set for this outcome

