- ii)     ii) how to position the sensor inside it,
- iii)     iii) how to move the object in order to reach the game’s target.

Once the sensor is worn or positioned inside an object, before starting the game, the patient is guided through a calibration phase to measure the sensors initial orientation in the space which acts as a reference position for all the movements recorded during the game. This process not only makes the measures more accurate but also nullifies any sensor wrongly positioned when worn (i.e. sensor overturning, rotations, inclinations respect to the body frontal plane).

In this pilot study investigators will recruit as many patients as possible as defined within the inclusion and exclusion criteria. There will be 75 devices available at the site from September 2018 to December 2019. Each patient will be provided with a WeReha device including the tablet and its charger, the inertial sensor and its charging station and cable, a kit of elastic straps together with a Velcro pocket and the 3 plastic objects. Every device can be used twice in order to assess as many patients as possible, providing a new set of straps and smart objects (that are to be considered single user only) and cleaning the other components by following specific and simple instructions provided by CoRehab.

Participants will be consented following a diagnosis of stroke and will keep the device for a maximum of 20 weeks following discharge from the hospital setting. This amount of time has been decided following review by clinicians and therapists during our earlier feasibility work. After that the tablet and the sensor will be collected, cleaned to ensure no cross contamination and meeting infection control guidelines within each Trust and made available for further use... The elastic straps with the pockets and the smart objects are the only personal and single use components, which will be disposed of after use... Secondary outcomes will only be assessed on “active patients”.

There will be a WeReha server available as a cloud solution, compliant with NCSC Cloud Security Principles, on which the web application will run and all the data will be collected whenever a patient’s device is connected to the internet. It is important to highlight that internet connection is not mandatory for the device to work properly as it will propose exercises to the patient as they were prepared initially after patient’s discharge. Then, whenever the device is

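### Enrolment counts by age-gender group are read as acceptance without a denominator, and a soft aim to balance the groups makes them harder still to interpret

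*Combined protocol and SAP*

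**What the plan says.** All references are to the combined protocol and SAP.

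- **Study goals and objectives** gives the enrolment count its meaning: "number of enrolled patients at the end of the trial period will be evaluated in order to understand the degree of acceptance". It then adds: "All previous measures will be evaluated in general and for 6 different age-gender groups". The count is therefore to be read group by group as well as overall.
- **Primary Outcome Measures** attaches a threshold ("Total number of patients enrolled -> KPI: minimum 50 patients enrolled") and defines the groups: "Age groups are: <55, 55-70, 70-85 both for male and female, for a total of six groups". It goes on: "Target would be to enroll patients within these groups as homogeneously as possible". The same sentence then removes any formal requirement: "but since we cannot foresee patients distribution there are no KPIs set for this outcome".
- **Study Design** gives a different instruction: "In this pilot study investigators will recruit as many patients as possible", within the entry criteria. There are 75 devices, each usable twice. Ward patients are pre-screened, and those who seem to qualify are passed to the recruiting therapist. A screening log tracks approaches, with reasons for ineligibility or refusal. The text does not say that the log holds age or sex, and no outcome uses it as a denominator.
- **Data Management and Statistical Analysis** plans no statistical analysis of the primary outcomes. They are judged against the KPIs, with no weighting.

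**The concern.** A count cannot be balanced on purpose across groups and also be evidence of how willing each group is. The more closely recruiters follow the balance aim, the more the six counts resemble one another, whatever the true willingness. Even if nobody follows it, a raw count mixes the number of eligible patients available with the share who said yes.

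The second consequence concerns the pooled results. If balancing raised the share of younger patients above their share of the eligible pool, and if younger patients used the device more, then the active-patient count, active weeks, minutes of exercise and questionnaire scores would look better than they would in the patients the service actually sees. These unweighted figures are what the study is judged on.

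**Working it through.** No sample-size formula lies behind the KPIs, so there is no planned figure to reproduce. The check has three parts.

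**1. What a group count can show.** For group g, enrolled = (eligible approached) × (acceptance). Only the left side is planned as an outcome. Suppose the counts came out equal and every eligible patient had been approached. Acceptance in each age band is then proportional to 1 / (that band's share of the eligible pool). Two assumed pools, for under 55 / 55–70 / over 70:

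| Assumed eligible mix | Under 55 relative to over 70 | 55–70 relative to over 70 |
|---|---|---|
| 10 / 20 / 70% | 70/10 = 7.0 | 70/20 = 3.5 |
| 25 / 47 / 28% | 28/25 = 1.1 | 28/47 = 0.6 |

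The same equal counts would mean acceptance seven times as high in the young, or nearly the same. If approaches were steered, equal counts would fit any pattern. This part needs no assumption about device use.

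**2. What full balance would do to the age mix.** At the KPI of 50 enrolled, equal groups give 50/6 = 8.3 per cell and 50/3 = 16.7 per age band. The share under 65 would be:

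- at least 1/3 = 33% (nobody aged 55–70 is under 65);
- about 1/3 + (10/15)(1/3) = 56% (ages uniform within 55–70);
- at most 2/3 = 67%.

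The Rationale section says: "Around 20% of stroke survivors are under the age of 65". That figure covers all survivors. The entry criteria select a narrower pool (first stroke, Modified Rankin ≤ 2, MoCA ≥ 12, caregiver available), and its age mix is not given. The only other age data are the 20 feasibility volunteers in Safety Considerations, with mean 63 and SD 12. Assuming a normal distribution, these give about 25 / 47 / 28% in the three bands and 57% under 65, close to the mix under equal groups.

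**3. Effect on a pooled usage rate, by assumption only.** Let the active share be 80% + g, 80% and 80% − g in the three bands. Equal groups give 80%. A pool with shares w1, w2, w3 gives 80% − g(w3 − w1), so the shift is g(w3 − w1).

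| g (points) | Survivor-like mixes, w3 − w1 = 0.50 to 0.65 | Feasibility mix, w3 − w1 = 0.03 |
|---|---|---|
| 0 | 0 | 0 |
| 5 | 2.5 to 3.3 points | about 0.1 |
| 10 | 5.0 to 6.5 points | about 0.3 |
| 15 | 7.5 to 9.7 points | about 0.4 |

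The survivor-like mixes run from 10/30/60 (0.60 − 0.10 = 0.50) to 5/25/70 (0.70 − 0.05 = 0.65). The shift can be nil or several points, and nothing in the documents says which.

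**The case against.** The balance aim is only a wish. It has no KPI, quota, cap or rule for turning patients away, and its own sentence concedes that the distribution cannot be foreseen. Study Design takes all comers, and 75 × 2 = 150 device uses against a minimum of 50 enrolled means that capacity forces no selection. Balanced groups are also a legitimate aim in a pilot that wants to describe subgroups before a later investigation. Weighting would be unstable: at an assumed 10% under 55, about 5 of 50 patients would be spread over two cells.

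All of this stands, and it rules out two stronger readings.

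- A reader might infer that the sample will be much younger than the patients treated and that the group counts will simply record steering. The documents describe no steering, and the 20% figure is for a different population from the eligible one.
- A reader might infer that age mix alone decides whether the KPI of 40 active patients is met. Take assumed active shares of 90 / 80 / 60%. Equal groups give 76.7%, and a 10/20/70 mix gives 67.0%. Forty active patients then need 40/0.767, so 53 enrolled, or 40/0.670, so 60 enrolled. The result differs only for 53 to 59 enrolled. With the feasibility mix the rate is 76.9%, practically the same as for equal groups.

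The objection leaves two things untouched: the group counts still lack a denominator, and the two recruitment instructions still differ with no rule for choosing between them.

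**Conclusion.** The point holds as a problem of interpretation. Enrolment by age-gender group, as planned, cannot show acceptance by group, because it has no denominator; this rests on no assumption. To the extent that recruiters act on the balance aim, the counts also reflect their effort.

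The effect on the pooled KPIs is a conditional risk of unknown size. It requires that balancing actually happens, that the eligible pool is older than an equal three-way split, and that use falls with age. Under the assumed values above it ranges from zero to just under 10 percentage points in the active share. The documents do not support a claim that the pooled verdict is wrong. The remedy is cheap and makes a stated primary outcome readable, so it is worth making.

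**What to change.** 1. Reconcile Primary Outcome Measures with Study Design: state that all eligible patients are approached and that enrolment is not balanced by group.
2. Add age band and sex to the screening log for every eligible patient approached, including those identified after discharge. First settle the bands: the top one ends at 85 in Primary Outcome Measures but is open-ended in Study goals and objectives and in the analysis section, and the inclusion criteria set no upper age limit.
3. Report acceptance as enrolled / eligible approached, overall and by group, using age and sex separately where the six cells are small (about 8 each at 50 enrolled, even if balanced).
4. Beside the pooled KPIs, show the age-sex mix of enrolled and of eligible patients. Add a version of the usage and questionnaire results weighted to the eligible mix, only as a sensitivity display and only where cells allow.

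The cost is two log fields, one reworded sentence and one extra table. The real downside is that, without balancing, the younger groups may be smaller and say less on their own.

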#### **Secondary Outcome Measures:**

- Barthel index and Modified Rankin Score: change from baseline (measured when receiving the device) at the end of the rehabilitation treatment (when returning the device)
- Time dedicated by the specialised personnel to each patient for training to learn the WeReha device before leaving the trial site (measured in minutes/patient)
- Number of calls per week for clinical and technical assistance specific for the WeReha device, registered on a paper or software spreadsheet by the sponsor

## Study Design

This is a pilot study to investigate acceptability of usage of technology to aid rehabilitation of post stroke patients at home. An innovative inertial sensor and interactive games based device, called WeReha, has been designed and developed to best meet the rehabilitation needs of stroke survivors... WeReha is composed of:

- i) an Android tablet running dedicated software
- ii) an inertial blue-tooth sensor with 3D accelerometer, 3D gyroscope and 3D magnetometer
- iii) a kit of elastic straps with a Velcro pocket to wear the sensor on specific body segments (chest, thigh, foot and wrist)
- iv) a kit of 3D printed plastic objects (a hourglass, a plate and a joystick) that become "smart" positioning tools through the use of sensors embedded inside them)

The WeReha software will present the patient with a series of rehabilitation exercises in the form of interactive games, using the worn sensor or the "smart objects". All the games in WeReha are based on the tracking the three dimensional movements of body segments or the smart objects through the sensor applied to them. The exercises integrated in WeReha have been designed with physiotherapists and clinicians, and are akin to traditional rehabilitation following a stroke that can involve any of the lower limbs (hip, knee and ankle) the upper limb (shoulder, elbow and wrist), the head and the trunk. Some require a sitting position, others a standing position with or without a support, according to the ability of the patient and whether there is supervision or not.

During an exercise which requires the worn sensor, a specific elastic straps among those of the kit has to be used. Dependent on the specific exercise sequence that will be performed; at startup the patient will be guided by the software step by step to:

- i) position the elastic strap around a specific body segment;
- ii) position the sensor inside the pocket;

- iii)     iii) Attach the pocket to the elastic strap. Particularly, the body segments involved in wearing the straps are the trunk, the thigh, the foot and the wrist, for balance, lower limb, foot-ankle and upper limbs exercises respectively.

A similar tutorial guides the patient on how to make the objects “smart” and thus trackable in the space and on how to use them correctly during games that simulate aspects of the real life. Specifically, the instructions provided include

- i)     what object to be used for the specific exercise;
- ii)     ii) how to position the sensor inside it,
- iii)     iii) how to move the object in order to reach the game’s target.

Once the sensor is worn or positioned inside an object, before starting the game, the patient is guided through a calibration phase to measure the sensors initial orientation in the space which acts as a reference position for all the movements recorded during the game. This process not only makes the measures more accurate but also nullifies any sensor wrongly positioned when worn (i.e. sensor overturning, rotations, inclinations respect to the body frontal plane).

In this pilot study investigators will recruit as many patients as possible as defined within the inclusion and exclusion criteria. There will be 75 devices available at the site from September 2018 to December 2019. Each patient will be provided with a WeReha device including the tablet and its charger, the inertial sensor and its charging station and cable, a kit of elastic straps together with a Velcro pocket and the 3 plastic objects. Every device can be used twice in order to assess as many patients as possible, providing a new set of straps and smart objects (that are to be considered single user only) and cleaning the other components by following specific and simple instructions provided by CoRehab.

Participants will be consented following a diagnosis of stroke and will keep the device for a maximum of 20 weeks following discharge from the hospital setting. This amount of time has been decided following review by clinicians and therapists during our earlier feasibility work. After that the tablet and the sensor will be collected, cleaned to ensure no cross contamination and meeting infection control guidelines within each Trust and made available for further use... The elastic straps with the pockets and the smart objects are the only personal and single use components, which will be disposed of after use... Secondary outcomes will only be assessed on “active patients”.

There will be a WeReha server available as a cloud solution, compliant with NCSC Cloud Security Principles, on which the web application will run and all the data will be collected whenever a patient’s device is connected to the internet. It is important to highlight that internet connection is not mandatory for the device to work properly as it will propose exercises to the patient as they were prepared initially after patient’s discharge. Then, whenever the device is

connected either through Wi-Fi or cellular network, data will be uploaded to the server through a secure VPN or https protected connection, or at the very latest when the device is returned to the hospital. However, for the sake of the study, we will provide a prepaid internet card to all participants requiring it. Patients data will be always uploaded and maintained in an anonymised form and stored following stringent security and privacy principles.

Data relative to the primary outcome will be collected automatically on the device and uploaded to the server whenever possible. Clinical measurements (such as scales and scores) will be assessed only when starting the study and when returning the device.

WeReha includes a password protected administration area accessible only by the dedicated figure, through which it is possible to manage the reset of data in the local memory once the device is collected and then re-assigned to another patient. In addition, every tablet is provided with a software program installed for a quick and effective remote assistance by the technical staff of the sponsor directly on the patient's WeReha device (Bomgar SW, [www.bomgar.com](http://www.bomgar.com)). This is intended as a second level support to patients and will only be required if the dedicated figure cannot solve the issue on which the assistance was sought. WeReha requires an internet connection at patient home in order to allow Corehab's remote intervention.

Following admission to Belfast or South Eastern Trust stroke units, patients will be pre-screened against the inclusion and exclusion criteria. Those who appear to fulfill the criteria will be highlighted by nurses and therapists to the recruiting therapist. Patients will be provided with all the study details and patient information sheet (PIS) to review. A screening log will be used to track the number of patients that are approached to participate. If the patient is ineligible or refuses to participate, the reason will be recorded in the log, if they so choose to provide us with reasons for the same.

In some cases, patients who have been discharged from the stroke units to the community may be identified as appropriate for the study. In this case the relevant Trust PI will provide them with the PIS and access for clarification.

